The placebo and inulin groups will receive pre-measured pots containing either the supplement or placebo powder for each week, along with scoops. Participants will be instructed to take either 2 or 3 scoops daily, depending on whether they are in the inulin or placebo group. They will also be provided with guidance on incorporating their daily dose into their diet, such as mixing it into smoothies or using it as a topping on yoghurts and breakfast cereals. Participants will be asked to maintain a daily dietary compliance record to track their supplement intake, including any missed doses and the reasons for not taking the supplement. If participants experience adverse effects, such as severe bloating or nausea, that prevent them from continuing with the supplement, they will be instructed to notify a member of the study team.

After the six weeks of interventions, all participants will fill in the same questionnaires and perform the physical tests, to enable evaluation. Participants and the researcher will meet in person twice: once at enrolment and again six weeks later.

OUTCOMES

Primary outcome:

- Numerical Rate Score (NRS) for pain to assess changes in response to the interventions.

Secondary outcomes:

- Changes in markers of pain assessed by quantitative sensory testing, and in markers of inflammation
- Changes in gut microbiome composition and serum levels of short chain fatty acids (SCFAs) in response to the interventions.
- Changes in functional outcomes (e.g., 30 second sit to stand test, get up and go test)

STATISTICAL ANALYSIS PLAN

The clinical trial data will be analysed using the appropriate parametric and non-parametric statistical tests, we will compare outcome measures (such as pain sensitivity and pain ratings) between the exercise and non-exercise groups while adjusting for baseline scores.

Secondary analyses (i.e., correlations between changes in SCFAs and changes in pain measures) will be conducted using the appropriate type of statistical test based on data normality (e.g., Spearman's).

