Data will be gathered during the first and last sessions of the INSPIRE trial. Trained local research personnel will compile all the data sources, and data entry in a RedCAP database will be done in a consistent manner. This will comprise data from QST, 30CST, and TUG as well as questionnaires. The data entry site will enter data from the clinical research forms (CRF) from the initial and final study visits.

ADVERSE EVENTS

Since the interventions in the current study are using components sourced from common foods and routine exercise, we foresee no adverse reaction or side effects. Increasing fibre intake may result in bloating amongst those who have a low habitual intake of dietary fibre. However, such effects are mild and not considered as a safety concern. Participants will be asked to record any side effects like bloating using the dietary compliance diary and will be advised to stop taking the supplement if they experience severe bloating. Between 2008 and 2017, 75,000 participants participated in these activities' trials, and no significant side effects were reported (Thorstensson, C. A. 2015 PMID: 25345913). An increase in back, hip, or knee pain is a remote possibility (Luan, L., 2022 PMID: 35091326). Using an online interface, we will track the patient's pain levels every week to see if there has been an increase in discomfort. The subject will be advised to discontinue

study participation and get in touch with their GP if their pain worsens to the point that they begin to struggle with everyday tasks.

Criteria for terminating the study: It is not anticipated that circumstances will arise that necessitate the termination of this study because it only consists of two assessments, does not involve investigational medications or medical devices, and the same intervention has not resulted in any serious adverse events in over 70,000 participants in Sweden.

Funding source

This study is funded by UKRI grant MR/W026813/1 and supported by infrastructure provided by the NIHR Nottingham Biomedical Research Centre (BRC).

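### Participants whose pain worsens badly are advised to leave the study, not just the intervention, and nothing keeps their week-6 NRS (minor; direction of any bias unknown)

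*Combined protocol and SAP*

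**What the plan says.** The primary outcome is pain on the NRS. The Adverse Events section says that an online interface will be used to track "pain levels every week to see if there has been an increase in discomfort". It then sets the rule for worsening pain, in a sentence that runs across a page break: "The subject will be advised to discontinue" followed by "study participation and get in touch with their GP if their pain worsens to the point that they begin to struggle with everyday tasks".

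The same section treats the supplement's main side effect differently. Participants "will be advised to stop taking the supplement if they experience severe bloating"; leaving the study is not mentioned.

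On data collection, Data Management says "Data will be gathered during the first and last sessions of the INSPIRE trial", and Description of Intervention says "Participants and the researcher will meet in person twice: once at enrolment and again six weeks later". Description of Intervention also says that after six weeks "all participants will fill in the same questionnaires and perform the physical tests, to enable evaluation".

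The Statistical Analysis Plan specifies an ANCOVA of the follow-up score with a four-level arm factor and the baseline score. On frequency, Adverse Events says "An increase in back, hip, or knee pain is a remote possibility" and gives no rate.

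**The concern.** The pain rule takes the participant out of the study as well as off treatment, and its trigger is worsening of the symptom that the trial measures. Someone who follows the advice between the two visits has a baseline NRS and, on the text as written, no assured follow-up NRS. The ANCOVA cannot use that person.

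The trigger is interim pain, a correlate of the week-6 score and not that score itself. Neither arm nor baseline captures it. Those who remain can therefore be a selected group, and selected differently by arm if exit rates differ. A week-6 score that was never sought cannot be recovered later.

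This point concerns the exit rule. A paragraph on missing-data methods would leave the rule in place.

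**Working it through.** **1. The text.** Three questions settle the reading.
- *Does the rule stop treatment or end participation?* It ends participation. The bloating rule in the same section shows that the authors can express the narrower action when they mean it.
- *Is follow-up after such an exit described?* No. The statement about all participants in Description of Intervention is a general scheduling line. It does not mention those advised to leave and does not clearly override that advice.
- *Is there other pain information?* Yes, the weekly online scores. They are described as monitoring, are not said to be the outcome NRS, and have no planned role in the analysis.

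**2. The plan's own power figure.** Sample Size and Justification gives 80% power for 0.51 SD with n=120, that is 60 v 60 for a main effect. At two-sided 5%: 0.51 × √(60/2) − 1.96 = 2.793 − 1.960 = 0.833, and Φ(0.833) = 79.8%. The figure reproduces. Fewer numbers alone matter little: the same formula gives 77.7% at 5% loss (57 per group) and 75.5% at 10% (54 per group).

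**3. Illustrative bias.** The only document input is the true exercise effect, 0.84 − 0.20 = 0.64 SD. The rest is assumed:
- baseline–follow-up correlation 0.5 and change SD 1, so follow-up = 0.5b + μ + e with Var(e) = 0.75;
- μ = −0.20 without exercise and −0.84 with it, already present at the interim check;
- interim rise in pain = −0.5b + μ + e′ (SD 1), with corr(e, e′) = 0.6;
- everyone whose rise exceeds the cut leaves.

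Exit probability is 1 − Φ(z), with z = cut + 0.20 (non-exercise) or cut + 0.84 (exercise). Cov(e, rise) = 0.6 × 0.75 = 0.45, so among those who stay the mean of e shifts by −0.45h, where h = φ(z)/Φ(z). Baseline adjustment does not remove this shift. Ignoring a small change in the baseline slope:
- rule acting in all arms: estimate = 0.64 − 0.45(h₀ − h₁);
- exits in exercise arms only: estimate = 0.64 + 0.45h₁;
- exits in exercise arms only, no true effect: false benefit = 0.45h₀ (the exercise arms then have μ = −0.20).

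| Cut (SD) | h₀ | h₁ | Exits, non-exercise v exercise (true 0.64, all arms) | All arms, true 0.64 | Exercise arms only, true 0.64 | Exercise arms only, true 0 |
|---|---|---|---|---|---|---|
| 1.0 | 0.219 | 0.076 | 11.5% v 3.3% | 0.575 | 0.674 | 0.099 |
| 1.5 | 0.098 | 0.026 | 4.5% v 1.0% | 0.607 | 0.652 | 0.044 |
| 2.0 | 0.036 | 0.007 | 1.4% v 0.2% | 0.627 | 0.643 | 0.016 |

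In the exercise-only columns, only the exercise arms lose people: 3.3%, 1.0% and 0.2% when the true effect is 0.64, and 11.5%, 4.5% and 1.4% when it is zero.

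Simulating the ANCOVA itself agrees: 0.571 / 0.607 / 0.627 in all arms, 0.673 / 0.650 / 0.641 with exits in exercise arms only, and a false benefit of about 0.10 / 0.045 / 0.01 under the null. With the same rule in all arms and no true effect there is no bias, and type I error is about 5%.

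**4. Sensitivity (all arms, true 0.64).** With interim and final residuals perfectly correlated: 0.526 / 0.585 / 0.618 at the three cuts. With half following the advice (correlation 0.6): 0.610 / 0.624 / 0.634. With five weekly checks and a 2.5 SD cut (exits 1.7% v 0.8%): 0.632.

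**5. Scale at rare exits.** The 2.0 SD row, with the rule in all arms, corresponds to 60 × 0.0139 + 60 × 0.0023 ≈ 1 participant of 120.

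**The case against.** The strongest reply is about materiality. The trigger is severe and the plan regards increased pain as unlikely. Exits that rare correspond to the 2.0 SD row or beyond, where the estimate moves by about 0.01 SD. The larger shifts need exit rates that no document supports. This stands, and it is why the point is minor.

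Second, the rule is advice, and nothing forbids collecting week-6 data afterwards. That also stands: the text leaves retention open and does not order that data be discarded. It still gives staff no instruction to keep these participants.

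Third, a reader might infer that pain is recorded at the two visits only, so that nothing is known about those who leave. The documents do not support that. Weekly online scores may capture the worsening, so the loss could depend partly on something observed and be partly recoverable. No such use is planned.

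Fourth, a reader might infer that the rule dilutes the treatment effect and costs power. That is not supported either. Dilution needs the rule to act in all arms and a treatment that works. The online interface for weekly tracking is not identified, and the only online platform described elsewhere is the exercise app, sent to the exercise groups. If exits occur mainly there, the estimate moves the other way. Any power loss beyond lost numbers depends on assumed correlations and exit rates.

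**Conclusion.** The point holds as a minor one. The protocol advises leaving the study on a trigger related to the primary outcome, no section retains the week-6 NRS for those who leave, and the ANCOVA does not adjust for interim pain. Loss of the primary outcome can therefore depend on pain during follow-up.

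The size cannot be determined from the documents. At exits of about 1% or less the bias is negligible, roughly 0.01 to 0.02 SD in the base model. It would reach about 0.07 to 0.10 SD only if some 11.5% left the non-exercise arms under a common rule, or left the exercise arms alone with no true effect. The direction is unknown. These figures rest on the assumed correlations, cuts and compliance above and illustrate the mechanism; they do not forecast this trial's bias.

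**What to change.** Replace the sentence in Adverse Events with: *The participant will be advised to stop the intervention and contact their GP, and will remain in follow-up.* Add that the week-6 NRS will be sought from everyone randomised, by phone or online if a visit is not possible, unless consent is withdrawn, and that participants are analysed in their allocated arm.

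The cost is one sentence of protocol wording and a few remote contacts. The safety advice is unchanged, and participants may still withdraw. The estimate then includes people who stopped the intervention, so it describes the effect of being allocated to it. A sensitivity analysis that assigns a poor outcome to those who stopped for pain and have no week-6 score is optional; the point does not depend on it.
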